Up to 315 participants will be enrolled to yield 300 participants with valid US-DOT data to evaluate the primary and secondary objectives as below.

Aim 1.1 Assess the impact of US-guided DOT on potential reduction of benign biopsies
The primary objective of this prospective study is to assess the impact of US-guided DOT on the potential reduction of benign biopsies, a.k.a, improve specificity. We hypothesize that the adjunctive use of US-guided DOT will reduce the rate of benign breast biopsy. Using these criteria, the first endpoint, specificity = $Gd/(Gb+Gd)$, will be calculated as the proportion of subjects with a negative assessment (BI-RADS 2 or 3) and with no cancer at biopsy. With the exception of a small minority of patients with BI-RADS 3 assessments who elect to undergo biopsy and who will be tracked separately, all subjects in this study are considered positive using the current SOC, because they have been recommended for biopsy. Hence, 1) the specificity in this group for the SOC is 0% by definition; 2) the estimate of specificity for the DOT system represents the improvement in specificity; and 3) the estimate of specificity is also an indication of the percentage of benign biopsies that might be avoided if the NIR data were used by the radiologist in the biopsy decision making process.

Aim1.2 Assess the impact of US-guided DOT as an adjunct to CI on maintaining high sensitivity
To also ensure that the potential for false negatives is not a significant risk with the use of the US-guided DOT, we will also assess the probability of potentially misclassifying a malignant abnormality. By definition, $FN=Gc/(Gc+Ga)$, which is 1 minus sensitivity. Our earlier study [Zhu reference] indicated that both radiologists reached 96.6% to 100% sensitivity with the tHb data included, and therefore had a 0-3.4% probability of missing a malignant lesion.

All CRFs including CI, DOT, CEM and biopsy results will be entered by our study radiologists, or study coordinator or study pathologist into the OnCore data base to be exported to [name] for statistical analysis. An ad hoc analysis of the CI, CEM and optical imaging characteristics and histopathologic features of false negative cases will be performed to identify suspicious features that always indicate a level of suspicion warranting biopsy.

Aim1.3 Explore the potential benefit of managing post biopsy BI-RADS 4C and 5 lesions

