Study Hypothesis 1 for aim 1.1: The first hypothesis is that the measured tHb distribution and values can be potentially used as an adjunct for radiologists to reduce unnecessary biopsies in low risk patients with benign pathological results. The benign biopsy spare rate can be calculated as $Gd/(Gb+Gd)$ in Fig.11, which is equivalent to the specificity, the primary endpoint of Aim1.1. We observed in previous studies that specificity could be improved by 45% on average if NIR data were used in the decision-making process. Note that the specificity in this group of biopsied patients under the SOC is 0% by definition. In this study, we conservatively set the minimum acceptable specificity at 30%. The null and alternative hypotheses, which demonstrate superiority when the NIR imaging data are used as an adjunct to the diagnostic assessment versus when the SOC diagnostic data are used alone, are given by

$$H_0: \text{Specificity} \leq 30\% \text{ versus } H_1: \text{Specificity} > 30\%$$

This aim will be considered a success if the lower limit of the 95% confidence interval on specificity exceeds 30%. This hypothesis will be tested at the one-sided 0.025 level, rather than 0.05, to account for the fact that two hypothesis tests (on specificity and sensitivity) are planned. This aim is considered a success if the lower limit of the 97.5% confidence interval on specificity exceeds 30%.

Study Hypothesis 2 for aim 1.2: The second hypothesis is that, while reducing unnecessary benign biopsies, the addition of adjunct information from US-DOT still maintains a high sensitivity

in capturing nearly all malignant tumors. This can be evaluated based on sensitivity, which is calculated as $G_a/(G_a+G_c)$, as shown in Fig.11.

H_0 : sensitivity $\leq 90\%$ versus H_1 : sensitivity $> 90\%$

Based on previous study, we anticipate the sensitivity will be in the range of 96-100%. This aim is considered a success if the lower limit of the 95% confidence interval for sensitivity is at least 90%. This hypothesis will be tested at the one-sided 0.025 level, rather than 0.05, to stringently account for the fact that two hypothesis tests (on specificity and sensitivity) are planned. This aim is considered a success if the lower limit of the 97.5% confidence interval for sensitivity is at least 90%.

10.3 Sample size justifications.

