We expect ~300 eligible women who will undergo SOC biopsy with valid US-DOT data and fall in the BIRAD categories of 3, 4A, 4B, 4C, or 5, rendering ~210 pathologically benign biopsies and 90 malignant biopsies. **For Study Hypothesis 1**, prior study results indicate the specificity was estimated to be no less than 45%. A total of 83 benign biopsies are needed to achieve 80.18% power to test Study Hypothesis 1 at a 2.5% level. This calculation is based on a 1-sided exact binomial test by conservatively assuming the true specificity is 45%, while 210 benign biopsies achieve 99.4% power to test Hypothesis 1. We also calculated the sample size based on the more stringent requirement that the lower limit of the 1-sided 97.5% conservative Clopper-Pearson binomial exact confidence interval (CI) (60) to the estimated specificity (of 45%) should exceed 30%. The 210 benign biopsies will allow us to estimate the 1-sided 97.5% exact CI to be between 37.7%~100%, thus satisfying this more stringent requirement. **For Study Hypothesis 2**, 90 malignant biopsies will achieve 89.33% power to conduct Study Hypothesis 2 at a 1-sided 2.5% level, based on a 1-sided exact binomial test. With 90 malignant biopsies, the sensitivity can be estimated at 98% with a 1-sided 97.5% exact CI of 92.06%~100%, thus satisfying the stringent criterion requiring a lower limit of >90%.

In calendar year 2016, over 7,000 women came to the Siteman Cancer Center at WashU for diagnostic evaluation. Approximately 17% had suspicious or highly suggestive malignancy findings and were recommended for tissue sampling. Over 700 women underwent US guided biopsy, which is more than 10 times larger than the potential study subjects each year.

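### The review of missed cancers under Aim 1.2 has no benign comparison group and too few cases to show that any feature always warrants biopsy

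*Combined protocol and SAP*

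**What the plan says.** Section 7 treats a combined conventional imaging (CI) and DOT assessment of BI-RADS 2 or 3 as test negative. Among the negatives, lesions malignant at biopsy form Gc (false negatives) and benign lesions form Gd (true negatives, the benign biopsies that might be avoided).

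Section 7.1, Aim 1.2, then plans an ad hoc analysis of the CI, CEM and optical characteristics and "histopathologic features of false negative cases will be performed to identify suspicious features that always indicate a level of suspicion warranting biopsy". It names no comparison group, method, minimum number of cases or validation step. Section 10.4 does not mention this analysis.

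The figures that determine how many cases there will be are in three places:
- Section 10.3 expects about 300 women, "rendering ~210 pathologically benign biopsies and 90 malignant biopsies", and says that "the sensitivity can be estimated at 98% with a 1-sided 97.5% exact CI of 92.06%~100"%.
- Section 10.2 states that "we anticipate the sensitivity will be in the range of 96-100"%.
- Section 7.1 reports that readers in the earlier study "therefore had a 0-3.4% probability of missing a malignant lesion".

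**The concern.** A feature is a useful warning against downgrading a lesion only if it is present in cancers that would be missed and uncommon in benign lesions that were correctly downgraded. The first frequency comes from Gc and the second from Gd. The planned review looks only at the first. It can list what the missed cancers had in common, but it cannot separate a warning sign from something most downgraded lesions also show.

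The stated aim is to find features that always point to biopsy, which is a statement about lesions carrying the feature. The benign lesions carrying it belong in that denominator. A recommendation drawn from Gc alone could send benign lesions back to biopsy, against the study's primary objective, and the review would not show that cost.

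**Working it through.** **1. The plan's own figure.** Section 10.3 says that "90 malignant biopsies will achieve 89.33% power to conduct Study Hypothesis 2 at a 1-sided 2.5% level". Inputs: n = 90, null sensitivity 0.90 (Section 10.2), one-sided α = 0.025, true sensitivity 0.98. The smallest success count r with P(X ≥ r | 0.90) ≤ 0.025 is r = 87, where the tail is 0.0169 (r = 86 gives 0.0465). Power = P(X ≥ 87 | 0.98) = 0.8933. The stated power reproduces, so 98% is the planning value. With 90 cancers and one result per lesion, Aim 1.2 succeeds only with at most 3 false negatives.

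**2. Expected false negatives, one result per lesion.** Expected count = 90 × (1 − sensitivity).
- At 98%: 90 × 0.02 = 1.8. From Binomial(90, 0.02): P(0) = 0.16, P(1) = 0.30, P(≤1) = 0.46, P(≤3) = 0.89.
- At 0–3.4% missed: 0 to 90 × 0.034 = 3.06.
- At 96–100% sensitivity: 0 to 90 × 0.04 = 3.6.

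**3. Three readers per case.** Section 7 assigns three readers to each case, and no rule for combining them is stated. At a 2% miss rate per read there are 270 × 0.02 = 5.4 false-negative reads. The number of distinct cancers runs from 1.8 (readers miss the same lesions) to 90 × (1 − 0.98³) = 5.3 (readers miss independently). The independent-reader figure is 90 × (1 − 0.966³) = 8.9 at 3.4% and 90 × (1 − 0.96³) = 10.4 at 4%.

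**4. What a shared feature can show.** If all k missed cancers have a feature, the exact two-sided 95% lower limit for its frequency among missed cancers is 0.025^(1/k).

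| k of k | Lower limit |
|---|---|
| 2 | 15.8% |
| 3 | 29.2% |
| 4 | 39.8% |
| 10 | 69.2% |

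These limits concern only how common the feature is among missed cancers. How often a lesion with the feature is malignant cannot be estimated from Gc at all.

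**5. Illustration of chance agreement (assumed inputs).** The documents do not give the number of candidate features or their prevalence. Assume 20 independent features unrelated to malignancy, each with prevalence f. The chance that at least one is shared by all k misses is 1 − (1 − f^k)^20.

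| f | k = 2 | k = 3 |
|---|---|---|
| 10% | 18% | 2% |
| 30% | 85% | 42% |
| 50% | over 99% | 93% |

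The result depends heavily on f. It shows that agreement among two or three cases is weak evidence, not how often the review would mislead.

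**6. What Gd would add.** At the planned 45% specificity, Gd holds 210 × 0.45 = 94.5, about 94 lesions. A feature in 30% of them has a frequency known to about ±1.96 × √(0.3 × 0.7/94) = ±9 percentage points, and would return about 28 lesions to biopsy. With 2 of 2 misses showing the feature, the two-sided Fisher p against Gd is 0.012, 0.046, 0.095 or 0.49 when 10%, 20%, 30% or 50% of Gd also show it. The comparison exposes common features, but it remains descriptive.

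**The case against.** The strongest reply is that this is one ad hoc sentence describing a clinical case review. Specificity and sensitivity come from the readers' recorded assessments and are tested by exact binomial methods in Section 10.4. No rule is fed back, no case is re-scored and no endpoint depends on the review. That stands. A reader might infer that the primary specificity result could be pulled towards its 30% floor. The documents do not support that, because they contain no step that applies these features to the trial's results.

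A second reply is that radiologists will look for features already thought suspicious rather than screen random variables. That also stands, and it limits the illustration in step 5. Experience may suggest which features to examine, but it does not supply their frequency in this study's downgraded benign lesions.

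A third reply is that Section 10.4 already compares malignant with benign lesions through ROC and tree-based models. That is only partly an answer. Those models use tHb and other optical parameters. They do not cover conventional imaging or CEM features, are not restricted to test-negative lesions, and are not linked to this review.

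Finally, with about two cases even the comparison with Gd has little power. That is true, and it is a further reason to drop the word always. The comparison still gives a usable estimate of the benign cost.

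**Conclusion.** The point holds as a limit on what the review can conclude. As written, it cannot show whether a feature of the missed cancers discriminates them from correctly downgraded benign lesions, and the expected number of cases cannot support a claim of always. The size is 1.8 expected misses with one result per lesion (16% chance of none), or about 1.8 to 5.3 distinct cancers with three readers at a 2% miss rate. Higher miss rates within the plan's own range raise the upper end to about 9 or 10, where ten of ten still has a lower limit of 69%. The count rests on 90 cancers and 98% sensitivity, and the ceiling of 3 under success rests also on one result per lesion.

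It would go too far to infer that the review will return features that do not discriminate. There may be no missed cancers, and a feature that is found may be a real warning sign; the review simply cannot tell. The two hypothesis tests are unaffected. The harm is confined to any biopsy recommendation drawn from this analysis.

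**What to change.** Amend the Aim 1.2 sentence and add a matching line to Section 10.4:
- Tabulate each candidate imaging feature (CI, optical, and CEM where it was done) in Gc beside Gd, with exact intervals for both frequencies.
- For each feature, give the number of missed cancers it would recover and the number of true negatives it would return to biopsy.
- State whether a false negative is counted per lesion or per read.
- Keep histopathologic features as description only. They are known only after biopsy, so they cannot by themselves indicate who needs one.
- Replace the claim that features always indicate biopsy with wording that calls the findings descriptive and hypothesis-generating.

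The cost is a change of wording and one small table. Section 7.1 already places the CRFs and biopsy results in one database. The documents say that the CRFs include a BI-RADS assessment but do not list individual features, so some abstraction for about 94 Gd lesions may be needed. Sample size, endpoints and tests do not change.

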To accomplish the aims of assessing the impact of adjunctive US-guided DOT on reducing benign biopsy recommendation (i.e. FPs), while maintaining sensitivity (i.e. TPs) we will conduct a reader study of the 300 subject trial. Three of four study radiologists will serve as study readers for each case. (To eliminate potential bias a study radiologist performing the biopsy will not serve as a reader for that case.) As noted above the study radiologist who performs or supervises the US-guided DOT exam will be one of the readers. Two additional study radiologist readers will subsequently and independently review the available pre-existing patient information and CI data, (excluding the US-guided biopsy exam) and complete CI and DOT CRFs blinded to the pathology result of the abnormality that underwent biopsy. The CRFs include a BI-RADS assessment. The reader will first complete the CI CRF blinded to the US-guided DOT result, then after reviewing the optical data (tHB concentration and distribution) the reader will complete the DOT CRF including the impact of US-guided DOT information on the BI-RADS assessment, i.e. no change, decreased or increased.

Similar to the CI plus DOT workflow, for cases that have CEM, a CI CRF will be completed first, followed by a CEM specific CRF including a BI-RADS assessment and the impact of CEM on the BI-RADS assessment will be recorded. As noted above, the study radiologist that supervises the US-guided DOT and CEM exams will serve as one of the study readers. For the subsequent two readers we will alternate which adjunctive modality (i.e. CEM or US-DOT) is reviewed first and separate the subsequent review of the second adjunctive modality by a minimum of 4 weeks to prevent recollection bias).

Figure 4 diagrams the core analysis. Combined CI and US-guided DOT BI-RADS 2 and 3 assessments will be considered test negative, and BI-RADS 4A, 4B, 4C, and 5 assessments will be considered test positive. For negative tests, the biopsy proven malignant group (Gc, see Fig. 1(b)) represents false negative results, and the benign group Gd represents true negatives and reflects the potential reduction in benign biopsy recommendation if US-guided DOT were used as SOC. Ga represent true positives and Gb represent false positives utilizing adjunctive US-guided DOT. A comparison of the Ga groups i.e. CI alone vs. CI & DOT will constitute the assessment of the effect of adjunctive US-guided DOT on sensitivity.

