From a total of 300 patients who undergo the US-DOT exam, we expect to recruit a small subset of patients with BI-RADS 4C or 5 lesions whose biopsy results are benign. We will correlate initial biopsy results, optical data and gold standard final pathology for this subset of patients. This pilot data will allow us to assess the potential benefit of US-guided DOT in managing discordant abnormalities, i.e. reducing additional invasive procedures of a subset of benign abnormalities.

Exploratory Aim 1.4 Explore and compare US-guided DOT and CEM
In this exploratory aim, we will evaluate the agreement (Kappa coefficient) of US-guided DOT and CEM, as both modalities measure alterations in lesion vascularity. We will compare BI-RADS assessments of CI&CEM vs. CI&US-guided DOT as well as correlate imaging data such as intensity of enhancement in CEM and the total hemoglobin level of US-DOT.

Alternative plan: *If US-guided DOT is not comparable with CEM we will evaluate the capability of US-guided DOT in improving the accuracy of combined CI&CEM because CEM may become SOC in a significant subset of patients.*

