10.4 Data Analysis

All data will be analyzed as it is without imputations. Summary statistics will be used to summarize data including mean, median, standard deviation, interquartile range for continuous data and count (percentage) for categorical data.

All evaluable subjects will be analyzed. In addition to the specificity and sensitivity of US-guided DOT results, PPV, NPV, and overall accuracy will be calculated. The two study hypotheses will be tested by a binomial exact test and by constructing the one-sided 97.5% Clopper-Pearson exact confidence intervals for specificity and sensitivity. The lower limit will determine the achievement of study goals. We will explore the data further to refine the classification algorithm and the cut-off threshold. ROC analysis will evaluate the quantitatively measured tHb for pathological results of malignant biopsies. Besides tHb and its distribution, other parameters (such as oxyHb, deoxyHb, and distributions) will be either linearly incorporated with tHb to maximize the ultimate area under ROC or non-linearly through a tree-based classification model (e.g., using the R package “rpart”) (62).

The area under the ROC will be calculated to gauge the model's overall discriminative ability for biopsy results.

For the exploratory study (discordant biopsy results), the imaging data (e.g., tHb, oxyHb etc) will be summarized as appropriate in the subset of participants whose BIRAD results yield highly suspicious abnormalities (BI-RAD 4C, 5) but pathology yield benign results. Two sample t-test or Wilcoxon rank sum test as appropriate will be applied to compare this subset versus those with a malignant biopsy.

For the exploratory Study (CEM DOT correlation), we will compare BI-RADS assessments of CI&CEM vs. CI&US-guided DOT as well as correlate imaging data such as intensity of enhancement in CEM and the total hemoglobin level of US-DOT using Pearson or Spearman correlation coefficients. We will evaluate concordance/disconcordance between US-guided DOT and CEM using agreement measure (Kappa coefficient) and will test the discordance using McNemar test.

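### The DOT–CEM kappa has no stated variable; if it is taken on combined BI-RADS, the shared conventional-imaging read can by itself produce apparent agreement

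*Combined protocol and SAP*

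**What the plan says.** Section 7.1, Exploratory Aim 1.4, states the purpose: "we will evaluate the agreement (Kappa coefficient) of US-guided DOT and CEM, as both modalities measure alterations in lesion vascularity". The next sentence reads: "We will compare BI-RADS assessments of CI&CEM vs. CI&US-guided DOT as well as correlate imaging data such as intensity of enhancement in CEM", the correlation being with tHb. An alternative plan (DOT added to CI and CEM) applies if DOT proves not comparable with CEM, and no criterion is given for that.

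Section 10.4 names the statistics: "We will evaluate concordance/disconcordance between US-guided DOT and CEM using agreement measure (Kappa coefficient) and will test the discordance using McNemar test". For the direct comparison it correlates CEM enhancement intensity with "the total hemoglobin level of US-DOT using Pearson or Spearman correlation coefficients".

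Section 7 describes how the ratings arise. For DOT: "The reader will first complete the CI CRF blinded to the US-guided DOT result", and the DOT form follows. For CEM: "for cases that have CEM, a CI CRF will be completed first, followed by a CEM specific CRF including a BI-RADS assessment". Both adjunct forms record the impact on the BI-RADS assessment; the three levels (no change, decreased, increased) are spelled out for DOT. For the two later readers the plan will "separate the subsequent review of the second adjunctive modality by a minimum of 4 weeks". It does not say whether the CI form is completed again for the second modality.

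**The concern.** Kappa corrects for the agreement expected from the marginal distributions. It does not correct for an input that both ratings share. Here each combined rating is the CI rating of the lesion, left alone or revised. A lesion that is BI-RADS 5 on CI will mostly stay 5 under both adjuncts, and the table fills along its diagonal whether or not tHb and contrast enhancement have anything in common.

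McNemar's test is no safeguard. It compares the two positive rates, so unrelated modalities that downgrade equally often satisfy its null hypothesis.

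At stake is what a moderate or high kappa would be taken to mean. The stated rationale is shared vascular information, but the figure could largely be CI agreeing with itself. It could also colour the undefined judgement of whether DOT is comparable with CEM.

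**Working it through.** The plan gives no target kappa, power or CEM subset size for this aim, so there is no figure to reproduce. The check asks what kappa results when DOT and CEM are unrelated given CI.

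**Inputs**
- From section 7: BI-RADS 2–3 is test negative and 4A–5 positive (stated for CI with DOT).
- From sections 1.1 and 10.3: 35% (12/35) and 45%, borrowed here as the chance that a 4A or 4B lesion is downgraded to 3.
- Assumed, not in the documents: a CI mix of 5% BI-RADS 3, 35% 4A, 25% 4B, 15% 4C and 20% 5; alternatively, one-category shifts in 20–50% of reads, three quarters of them down.

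**Formula.** The joint table is the sum over CI category c of P(c) × P(DOT read | c) × P(CEM read | c). Kappa = (Po − Pe)/(1 − Pe).

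**Worked case: each modality independently downgrades 35% of 4A/4B (60% of lesions)**
- Multi-category: Po = 0.40 + 0.60 × (0.35² + 0.65²) = 0.727. The marginals for 3, 4A, 4B, 4C and 5 are 0.26, 0.2275, 0.1625, 0.15 and 0.20. Pe is the sum of their squares, 0.208. Kappa = (0.727 − 0.208)/0.792 = 0.66.
- Positive/negative: Pe = 0.26² + 0.74² = 0.615. Kappa = (0.727 − 0.615)/0.385 = 0.29.
- Positive/negative without BI-RADS 3: the negative rate is 0.21/0.95 = 0.221, Po = 0.713 and Pe = 0.656. Kappa = 0.17.
- Impact item, unstratified: the rate of decrease is 0.21. Pe = 0.21² + 0.79² = 0.668. Kappa = (0.727 − 0.668)/0.332 = 0.18.
- Impact item within 4A/4B: Po = Pe = 0.545. Kappa = 0.
- McNemar: both discordant cells equal 0.60 × 0.35 × 0.65 = 0.1365, so its null hypothesis is exactly true.

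**Both rules over their ranges, unrelated modalities**

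| Kappa on | One-category shifts, 20% to 50% | 4A/4B downgrades, 35% to 45% |
|---|---|---|
| BI-RADS, unweighted | 0.59 to 0.29 | 0.66 to 0.62 |
| BI-RADS, quadratic | 0.89 to 0.78 | 0.86 |
| Positive/negative, 5% BI-RADS 3 | 0.48 to 0.39 | 0.29 to 0.32 |
| Positive/negative, no BI-RADS 3 | 0.10 to 0.27 | 0.17 to 0.23 |
| Impact item, unstratified | 0.00 to 0.01 | 0.18 to 0.25 |

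**Sensitivity to the assumptions**
- Three other CI mixes spanning the categories up to 5, with 20–45% of 4A/4B downgraded: unweighted 0.49–0.76, quadratic 0.81–0.90. One-category shifts in the same mixes: unweighted 0.20–0.44, quadratic 0.65–0.84.
- Any 4A–5 lesion allowed to drop straight to 3 at 35%: unweighted 0.38–0.41, quadratic only 0.27–0.35.
- A subset of 4A/4B lesions only: unweighted 0.09–0.49.
- CI read afresh for the second modality with 10–30% one-category disagreement (mix 3/42/20/15/20%, 4A/4B downgrades of 35–45%): unweighted 0.45–0.58, quadratic 0.81–0.85. A fresh read therefore does not remove the artefact.
- Simulated tHb and CEM intensity, generated as unrelated: correlation 0.00 in each of these re-read runs.

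**The case against.** The strongest reply is that the plan never says kappa will be taken on BI-RADS categories. Comparing BI-RADS assessments is a separate sentence in Aim 1.4, and pairing kappa with McNemar's test, which in its usual form needs paired binary data, suggests positive/negative. On that reading the artefact is slight to fair, especially as the BI-RADS 3 lesions that push it up are to be tracked separately. This stands. A reader might infer that the plan has chosen a multi-category kappa, or a weighted one; the documents do not support that. The defect is an unnamed variable whose most natural candidate is vulnerable.

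Second, the comparison at biomarker level is already planned. Section 2 singles out tHb concentration, section 7 names the presence and intensity of enhancement, and section 10.4 provides the correlation. Unrelated biomarkers should show up there. This also stands, but the plan does not say which result prevails if kappa and the correlation point in different directions.

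Third, agreement between combined reads is a legitimate question, because both modalities are studied as adjuncts to CI. True, but it is a different question from shared vascular signal, which is the reason given for the kappa.

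Fourth, kappa on the impact item is not automatically clean. That is correct: unstratified, it reaches about 0.2 in the 4A/4B-downgrade case, because CI category determines who can change.

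**Conclusion.** The concern holds in limited form. With unrelated modalities, a multi-category BI-RADS kappa can be about 0.3–0.7 unweighted and 0.8–0.9 quadratic-weighted. A positive/negative kappa can be about 0.1–0.3 without BI-RADS 3 lesions and up to about 0.5 with 5% of them. These sizes rest on the assumed CI mix and on changes that are one-category or confined to 4A/4B; other patterns of change give lower values, as shown.

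A reader might go further and conclude that an inflated kappa will wrongly block the alternative plan. The documents do not support that: no kappa threshold is attached to it, and it only adds an analysis within an exploratory aim. No primary or secondary conclusion is affected. The change is worth making because the same unrelated data can give anything from near 0 to about 0.9, depending on a choice that the plan leaves open.

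**What to change.** In Aim 1.4 and section 10.4:

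1. Calculate the DOT–CEM kappa on the recorded impact item (decreased, no change, increased) within CI BI-RADS category, or pooled across CI strata. Do not rely on the unstratified version. State that the CEM form uses the same three levels as the DOT form.
2. Report the combined BI-RADS kappa as descriptive only, with its categories and weighting named, beside the value expected if the modalities were independent given CI.
3. Base the judgement that DOT is comparable with CEM on the CI-stratified kappa and the already planned tHb–enhancement correlation, and write down the criterion.
4. Optionally, add a kappa of enhancement present/absent against tHb below or above the section 1.1 threshold, if enhancement presence is captured; the documents do not show that it is a form field.

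The cost is a few sentences and a few lines of analysis, since the impact item is already recorded for both modalities. The price is precision: a stratified kappa in a CEM subset of unstated size will be imprecise, and strata where no reading changes contribute nothing to it.
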